ASSOCIATION OF PLACENTA REMOVAL METHOD AND
POSTPARTUM LEUCOCYTOSIS

HNEAH KAEK 2019/KK/10

March 2020

STUDY PROTOCOL

OBJECTIVES

Cesarean section is one of the most common major abdominal operation in women worldwide and its rate is increasing every year. Although cesarean birth is considered as safe, it is a potentially morbid procedure with associated risks of hemorrhage, thromboembolic events, infection, and anesthesia risks. The incidence of postpartum infection has been estimated to be 1-4% after vaginal delivery and 10-20% after cesarean section. Manual removal of the placenta is widely accepted by surgeons worldwide. This method enables the surgeon quick intervention. Beside, it helps uterine cavity to be examined for damage and the presence of placental remnants. However, manual removal of the placenta is still a conflicting issue due to the risk of post-partum endometritis, post-partum hemorrhage and abnormal placentation in subsequent pregnancies. It is assumed that controlled cord traction reduces the risk of postpartum hemorrhage and infection.

The aim of this study is to examine whether there is an association between the method of removal of the placenta and increase in postpartum white blood cell counts

DESIGN

After informed consent, all patients are randomized according to the removal of placenta from the uterus after childbirth; manually (Group 1) or controlled cord traction without putting hands inside the uterus (Group 2). Patients are examined regarding to maternal infection. BMI measurement, obstetrics and medical history are recorded. The operative procedures are similar in all patients and followed the same technical steps. All the patients are asked to come to control on postpartum day 10.

METHODS

In both groups, oxytocin and a first-generation cephalosporin antibiotic are administered intravenously after the delivery of the infant. All uterine incisions were low transverse and all were closed without exteriorisation of the uterus. Complete blood count before delivery, on postpartum day 1 and 2, fever during hospitalisation, average blood loss during operation and the endometritis cases are recorded. All the patients are asked to come to control on postpartum day 10. Also, patients are asked to come to control if they have fever, abnormal vaginal bleeding, abnormal vaginal discharge, general feeling of sickness and pain in the pelvis. Fever is defined as a temperature above 38.5°C on two consecutive days, excluding the first 24 hours.

No Intervention: control group

In group 1, placenta is removed manually. Manual removal of the placenta will be performed by placing surgeon's dominant hand in the uterine cavity and removing the placenta by detaching it from the uterine wall as soon as possible after the delivery of the infant. The emptiness of the uterine cavity is verified manually.

Experimental: Study Group

In group 2, placenta is removed by controlled cord traction. Spontaneous removal will be performed by external uterine massage and traction on the umbilical cord are performed to assist spontaneous delivery of the placenta.

Primary Outcome Measure:

1. Change from baseline leukocyte level at postpartum day 1

Complete blood count is measured before delivery and postpartum day 1.

2. Detection of leukocyte count

Complete blood count is measured on postpartum day 2.

3. Detection of number of patients with fever

Body temperature is measured 4 times in a day. Highest temperature will be recorded on postpartum day 1 and 2.

5. Number of patients with postpartum endometritis

All the patients are asked to come to control on postpartum day 7. Also, patients are asked to come to control if they have fever, abnormal vaginal bleeding, abnormal vaginal discharge, general feeling of sickness and pain in the pelvis.

Secondary Outcome Measures:

Average blood loss during cesarean section is calculated by change from baseline hematocrit level at postpartum day 1.

Inclusion Criteria:

18-45 years old females

Nonanemic pregnancies

Singleton pregnancies

Elective cesarean sections

Exclusion Criteria:

Gestational age less than 34 weeks

Patients having umbilical cord prolapse,

Patients having placenta previa

Intrapartum fever and suspected chorioamnionitis

Patients having maternal infection

Patients having multiple gestation

Patients having antepartum hemorrhage

Patients having severe pre-eclampsia

Patients having placenta previa

Patients having placental abruption

Patients having uncontrolled gestational diabetes

Heart disease

Liver disorders

Renal disorders

Coagulopathy

Sample size determination formula*;

$$n = \frac{Nt^2pq}{d^2(N-1) + t^2pq}$$
$$n = \frac{(720)(1.96)^2(0.5)(0.5)}{(0.05)^2(720-1) + (1.96)^2(0.5)(0.5)}$$

The minimum number of patients to collect is 251.

* Yamane Taro (2010), Elementary Sampling Theory, Literatur publish, 3rd Edition

Statistical Analysis Plan

The study was approved by the Ethics and Clinical Investigation Committee. Statistical Package for the Social Sciences (SPSS; Version 20.0, Chicago, IL, USA) will be used for statistical analyses. Descriptive statistics will be presented as mean \pm standard deviation (SD) for normally distributed data, and as counts and percentages for categorical data. The relationship between the categorical variables will be examined using the Chi-square test and Fisher Exact Test. Results will be evaluated with a confidence interval of 95%, and $p < 0.05$ / $p < 0,01$ will be considered statistically significant. Kolmogorov-Smirnov test will be used for the assessment of the normality of data. Mann-Whitney U test will be used for the data not normally distributed.

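### The secondary outcome is named operative blood loss but is a hematocrit change to postpartum day 1: rename it and adjust for the pre-delivery value

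*Combined protocol and SAP*

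**What the plan says.** The only entry under Secondary Outcome Measures is: "Average blood loss during cesarean section is calculated by change from baseline hematocrit level at postpartum day 1". No formula, blood volume or unit accompanies it.

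METHODS schedules the blood counts: "Complete blood count before delivery, on postpartum day 1 and 2". The same sentence continues with other items: "fever during hospitalisation, average blood loss during operation and the endometritis cases are recorded". It does not say how operative loss is obtained.

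The Statistical Analysis Plan has no rule specific to this outcome. For continuous data the only between-group test it names is this: "Mann-Whitney U test will be used for the data not normally distributed". Transfusion and intravenous fluid volumes are not among the items listed for recording.

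**The concern.** The name and the measurement differ in two ways.

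- **Quantity.** The name is a loss of blood. The measurement is a change in a concentration, in percentage points, and nothing in the plan turns one into the other.
- **Window.** The name is limited to the operation. The measurement runs from the pre-delivery sample to postpartum day 1, so it also takes in later bleeding, fluid given, postpartum fluid shifts and any transfusion before the second sample.

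This matters because OBJECTIVES gives hemorrhage as one reason why manual removal is disputed, and says that cord traction is assumed to reduce it. If the plan is followed as written, a null hematocrit comparison would be reported as no difference in operative blood loss, and a positive one as an effect on operative blood loss. The data measure neither.

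A second, smaller matter is precision. The pre-delivery hematocrit is already collected, and a raw change score makes less efficient use of it than adjustment does.

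**Working it through.** **The plan's own figure.** The sample size formula with N = 720, t = 1.96, p = q = 0.5 and d = 0.05 gives 691.488 / 2.7579 = 250.73, which rounds up to the stated 251. It does not involve hematocrit or blood loss, so nothing below changes it.

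The documents give no hematocrit, blood volume, correlation or transfusion figures. All such inputs below are assumptions.

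**1. Conversion to volume.** Two simple conversions of a fall from H0 to H1 with blood volume V are V(H0 − H1)/H0 and V ln(H0/H1). For a fall from 36 to 33:

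| V (mL) | Linear (mL) | Logarithmic (mL) |
|---|---|---|
| 4500 | 375 | 392 |
| 5500 | 458 | 479 |
| 6500 | 542 | 566 |

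The same 3-point fall therefore stands for 375 to 566 mL, depending on choices the plan does not make.

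**2. Window.** Take V = 5.5 L, H0 = 36 and H1 = 36·exp(−loss/V)/(1 + dilution).

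| Operative loss (mL) | Later loss (mL) | Change in blood volume | Fall (points) | Loss implied by V ln(H0/H1) (mL) |
|---|---|---|---|---|
| 500 | 0 | 0 | 3.1 | 500 |
| 500 | 200 | 0 | 4.3 | 700 |
| 700 | 0 | 0 | 4.3 | 700 |
| 500 | 0 | +5% | 4.7 | 768 |
| 500 | 0 | −5% | 1.4 | 218 |

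Rows 2 and 3 cannot be told apart. Rows 4 and 5 show how far one woman's value moves with fluid balance alone.

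**3. What survives in the comparison of arms.** Fluid shifts of equal size in both arms mostly cancel. With V = 5 L and H0 = 36, losses of 0.5 L and 0.7 L differ by 36·(exp(−0.10) − exp(−0.14)) = 1.28 points. If both arms also gain 0.5 L of plasma, the difference is 1.28 × 5/5.5 = 1.16 points. That is about 9% shrinkage and no spurious effect.

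**4. Transfusion before the day-1 sample.** Take true falls of N(5, 2.5²) and N(4, 2.5²), a true difference of 1.0 point, with k points restored in women whose fall exceeds a threshold. The observed difference is 1 − k(P1 − P2), where P1 and P2 are the proportions above the threshold.

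| Threshold (points) | P1 | P2 | k = 3 | k = 6 |
|---|---|---|---|---|
| 8 | 11.5% | 5.5% | 0.82 | 0.64 |
| 10 | 2.3% | 0.8% | 0.96 | 0.91 |

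The observed difference is 64% to 96% of the truth over these settings.

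**5. Raw change against baseline adjustment.** With variance σ² at both times and correlation r, the change score has variance 2σ²(1 − r) and the adjusted day-1 value has σ²(1 − r²). The ratio is 2/(1 + r), which is 2/1.5 = 1.33 at r = 0.5 and 2/1.7 = 1.18 at r = 0.7. The raw change thus gives up 1 − (1 + r)/2 of the sample's information: 25% at r = 0.5 and 15% at r = 0.7.

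**The case against.** The best defence is that the protocol openly states a surrogate. METHODS says that operative loss is recorded, and the outcome sentence then says how it is derived. Allocation is randomized, the operative steps are said to be alike, and both arms receive oxytocin, so a difference in hematocrit fall can be attributed to the removal method. The hazard raised in OBJECTIVES is postpartum hemorrhage, for which a window to day 1 is arguably suitable. Most of this stands. It defends the measurement, but not the name.

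Three stronger readings are tempting and should not be drawn.

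- *METHODS and the outcome section contradict each other.* METHODS states no measurement method, and the outcome sentence can be read as defining the recorded item. Listing that item apart from the blood count leaves it unclear whether a direct measurement exists. That is an ambiguity.
- *Blood loss is not estimated at all.* It is approached indirectly, through a surrogate whose conversion is left unspecified.
- *Transfusion biases the comparison.* This depends on a transfusion rate that the documents do not give. The population is elective and nonanemic, with previa, abruption, antepartum hemorrhage and coagulopathy excluded, and only transfusions before the day-1 sample count. Moving the assumed threshold from 8 to 10 points removes most of the attenuation.

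The objection that an unadjusted change score is unbiased under randomization is also correct. Baseline adjustment is a gain in efficiency and does not correct an error.

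**Conclusion.** The point holds as a mismatch between the outcome's name and its measurement, together with a precision gain that is nearly free. Day-1 hematocrit can be validly compared between the arms, but the result is not a comparison of blood lost during the operation and should not be reported as one.

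The mismatch in unit and window follows from the plan's text and needs no assumption. The precision gain (variance ratio 1.33 at r = 0.5, 1.18 at r = 0.7) assumes equal variances at both times and an r that the documents do not give. The volume, dilution and transfusion figures are illustrations only. This is a secondary outcome: the 251, the primary outcomes and the stated aim concerning white cell counts are untouched.

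**What to change.** 1. Rename the secondary outcome as hematocrit on postpartum day 1, adjusted for pre-delivery hematocrit. In the Statistical Analysis Plan, specify ANCOVA with arm and pre-delivery hematocrit as terms, reporting the adjusted mean difference with its 95% confidence interval. State that the result will not be described as blood loss during the cesarean section.
2. Say in METHODS whether operative blood loss is measured directly. If it is, give the method and analyse that value under the blood-loss name. If it is not, remove it from METHODS as a separate item.
3. Optionally, if transfusion is recorded, report it by arm and add a rank-based sensitivity analysis that places women transfused before the day-1 sample as worst; the Mann-Whitney test already named in the plan would serve. Do not substitute the last hematocrit before transfusion. The only scheduled earlier sample is the baseline, so a woman who bled heavily would be given a fall of zero.

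Items 1 and 2 cost a few sentences and one regression on values already scheduled for collection. Item 3 needs transfusion status, which is not among the listed recorded items and may have to be added. What the trial gives up is a claim about operative blood loss that the hematocrit data could not support.

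### The minimum of 251 patients comes from a survey-precision formula for one proportion and does not size the two-arm randomised comparison

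*Combined protocol and SAP*

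**What the plan says.** The section headed Sample size determination formula computes n = N·t²·p·q / [d²(N−1) + t²·p·q] with N = 720, t = 1.96, p = q = 0.5 and d = 0.05, cites a sampling-theory textbook, and ends: "The minimum number of patients to collect is 251". It does not explain what the 720 are, or say whether 251 is the total or the number per arm.

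The other sections describe a different kind of study:

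- DESIGN: "all patients are randomized according to the removal of placenta from the uterus after childbirth", with two groups, manual removal and controlled cord traction. No allocation ratio is given.
- Primary Outcome Measure: the first item is "1. Change from baseline leukocyte level at postpartum day 1". The day-2 leukocyte count, fever and endometritis follow under the same heading.
- Statistical Analysis Plan: "The relationship between the categorical variables will be examined using the Chi-square test and Fisher Exact Test"; "Mann-Whitney U test will be used for the data not normally distributed". No test is named for normally distributed continuous data. Significance has two thresholds: "and $p < 0.05$ / $p < 0,01$ will be considered statistically significant".

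No section gives a target difference between arms, a leukocyte SD, event rates by arm, power or an allowance for loss.

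**The concern.** A sample size formula should match the question the trial asks. This one answers a survey question: how many women must be sampled from 720 to estimate a single percentage to within 5 points. The trial asks whether two randomised groups differ in leukocyte change. The 5 points in the formula is a margin of error for one proportion, so it is not a target difference and corresponds to no comparison in the trial. The finite-population correction also has no role in comparing randomised arms.

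This is the only justification offered for the trial size. A reader cannot learn from it what leukocyte difference the trial could detect, and so cannot interpret a null result. The same holds for fever and endometritis, where events may be few and a non-significant result could easily be misread as showing that the methods are equivalent.

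**Working it through.** **1. The plan's own figure.** With the inputs from the sample size section:

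- Numerator: 720 × 1.96² × 0.25 = 691.488
- Denominator: 0.0025 × 719 + 1.96² × 0.25 = 1.7975 + 0.9604 = 2.7579
- n = 691.488 / 2.7579 = 250.73, rounded up to 251. The stated figure reproduces.

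Without the finite-population correction, n = 0.9604 / 0.0025 = 384.16, rounded up to 385. The unexplained 720 therefore lowers the formula's own answer by about 35% (1 − 251/385).

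**2. What 251 gives for leukocyte change.** Everything from here on rests on my assumptions, because the plan states none of the inputs: 251 is the total, tests are two-sided, power is 80%. The detectable difference in SD units solves power = 0.80 for a two-sample t-test (noncentral t, noncentrality = difference / √(1/n₁ + 1/n₂)). For Mann-Whitney the sample is scaled by a relative efficiency of 0.955, its value for normal data.

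| Scenario | n₁/n₂ | alpha 0.05 | alpha 0.01 |
|---|---|---|---|
| 1:1, no loss | 126/125 | 0.355 SD | 0.434 SD |
| 1:1, 10% loss | 113/112 | 0.375 SD | 0.459 SD |
| 2:1, no loss | 167/84 | 0.376 SD | 0.460 SD |
| 1:1, Mann-Whitney | 126/125 | 0.363 SD | 0.445 SD |

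The choice between the plan's two thresholds moves the answer more than allocation, loss or choice of test does.

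**3. What 251 gives for fever and endometritis.** The documents give no expected rates for these outcomes as defined. The OBJECTIVES section cites infection incidence of "1-4% after vaginal delivery and 10-20% after cesarean section", but that is postpartum infection in general. The trial's fever definition is narrower, requiring a raised temperature "on two consecutive days, excluding the first 24 hours". I therefore take 2% to 20% as an assumed range, with the cited caesarean figures as its upper part.

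The 95% half-width for the difference, at a common rate p, is 1.96 × √[p(1−p)(1/126 + 1/125)]:

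| Assumed rate | Half-width |
|---|---|
| 2% | ±3.5 points |
| 4% | ±4.8 points |
| 10% | ±7.4 points |
| 20% | ±9.9 points |

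The 2% figure is rough, since it rests on about 2.5 expected events per arm.

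Power at alpha 0.05 with 126/125, by the pooled z-test and by full enumeration of Fisher's exact test:

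| Rates | Pooled z | Fisher |
|---|---|---|
| 20% v 15% | 18% | 15% |
| 15% v 10% | 22% | 18% |
| 10% v 5% | 32% | 24% |
| 4% v 2% | 15% | 7% |
| 20% v 10% | 60% | 55% |

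**The case against.** The strongest objection is that no shortfall has been shown. The arithmetic is right, and without an SD or a relevant difference nobody can say that 251 is too few; it might be ample. That stands. The point is that the justification does not fit the design, not that the trial is too small.

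Four narrower objections have some force:

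- *Total or per arm.* The figures above read 251 as the total. That is the natural reading, because the formula draws one sample from 720, but the protocol does not say so. With 251 per arm, the detectable difference would be about 0.25 SD (alpha 0.05) or 0.31 SD (alpha 0.01). The sponsor should state which applies; the formula is unsuitable either way.
- *Test.* The t-test figures assume a test that the SAP does not name. The Mann-Whitney figures, for a test it does name, are nearly the same.
- *Choice of contrasts.* Differences of 2 to 5 points are bound to show low power. Doubling the rate from 10% to 20% raises power to 60% or 55%, which is still below 80%.
- *Loss.* Loss to follow-up is more likely to affect endometritis, which depends on women returning after discharge, than a day-1 blood count. With 113/112 the half-widths widen to about ±3.7, ±5.1, ±7.8 and ±10.5 points, which does not change the picture.

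It can also be said that restating what 251 detects describes the size without justifying it. That is true until the sponsor adds the difference considered relevant, so the fix asks for it.

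**Conclusion.** The concern holds and should be corrected. The sample size rests on a one-sample precision formula that does not apply to a randomised two-arm comparison, and the documents give no other basis for it. This is a wrong method, not a missing detail and not an arithmetic slip.

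If 251 is the total, allocation is 1:1 and data are complete, the trial has 80% power for about 0.36 SD in day-1 leukocyte change at two-sided alpha 0.05, or 0.43 SD at 0.01. Across the allocation, loss and test scenarios checked, the range is 0.36 to 0.38 SD and 0.43 to 0.46 SD. Whether that is adequate depends on an SD and a relevant difference that only the sponsor can supply. For fever and endometritis, power is 7% to 32% for the differences of 2 to 5 points examined, so a non-significant result there would not be evidence of no difference. The event rates behind those figures are assumptions.

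**What to change.** Delete the survey formula and the correction for a population of 720. In their place state:

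- whether 251 is the total, and the allocation ratio;
- one significance level, and that it is two-sided;
- the expected loss;
- the test for day-1 leukocyte change;
- the leukocyte SD with its source, and the difference considered relevant.

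Then restate what the number delivers, for example:

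> With 251 patients in total, allocated 1:1, complete data and two-sided alpha 0.05, the trial has 80% power to detect a difference of about 0.36 SD in day-1 leukocyte change, i.e. [x] cells/µL for an SD of [y] (source). The difference considered relevant is [z] cells/µL.

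If 0.01 is the level kept, the figure is about 0.43 SD (0.44 with Mann-Whitney). For fever and endometritis add:

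> Expected rates are not known. At assumed rates of 2%, 4%, 10% and 20%, the 95% half-width for the difference between arms is about ±3.5, ±4.8, ±7.4 and ±9.9 points. A non-significant result on these outcomes will not be taken as evidence of no difference.

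The cost is protocol wording, one sourced SD and one stated target difference. No additional patients are requested. The drawback for the sponsor is that the justification becomes less favourable, and the detectable difference may turn out larger than the one considered relevant.

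### Four primary outcomes with no success rule or multiplicity control: if any one counts at 0.05, the false positive chance is roughly 8–19%, not 5%

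*Combined protocol and SAP*

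**What the plan says.** Under the heading Primary Outcome Measure the protocol lists four items:

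- "1. Change from baseline leukocyte level at postpartum day 1"
- "2. Detection of leukocyte count" (measured on day 2)
- "3. Detection of number of patients with fever"
- "5. Number of patients with postpartum endometritis"

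The numbering runs 1, 2, 3, 5, so four is the number of items visible. Blood loss is listed separately as secondary. The Objectives section states the aim as finding out whether there is "an association between the method of removal of the placenta and increase in postpartum white blood cell counts".

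The Statistical Analysis Plan is one paragraph of general methods. For categorical data it says: "The relationship between the categorical variables will be examined using the Chi-square test and Fisher Exact Test". It names Mann-Whitney for non-normal data. On significance it says "p < 0.05$ / $p < 0,01$ will be considered statistically significant", in a sentence that also sets the confidence level at 95%. Neither the protocol nor the plan names a lead outcome, a success rule, a testing order, a division of alpha or an adjustment for multiple tests.

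**The concern.** With four primary outcomes and no rule for combining them, nothing in the plan prevents the trial from being called positive because one of the four falls below the threshold. That gives four chances of a false positive, not one. A reader of the eventual report could not tell whether the outcome put forward was the one meant to answer the question or the one that happened to be significant.

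The aim concerns white blood cell counts, yet two of the four primary outcomes are not leukocyte measures, and the two that are have no order between them.

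The significance sentence also prints two thresholds, 0.05 and 0.01, without saying what each is for. This is a smaller matter, but the error rate depends on the reading.

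**Working it through.** **Inputs from the documents.** Four primary outcomes, two continuous and two binary; thresholds 0.05 and 0.01; 95% confidence; chi-square and Fisher tests for binary data; 251 patients in total.

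**Assumptions, because the documents give no figure.** Two-sided tests; a 126/125 split; leukocyte test correlation ρ of 0, 0.5 or 0.8; the same event rate for fever and endometritis, from 1% to 15%; these two independent of each other and of the leukocyte tests. No true difference on any outcome, and any one significant result counts as success.

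**The plan's own figure.** It states no family-wise error rate. Its sample size does reproduce: 720 × 1.96² × 0.25 / (0.05² × 719 + 1.96² × 0.25) = 691.488 / 2.7579 = 250.73, rounded up to 251. The formula estimates a single proportion and has no term for multiple outcomes.

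**Simple limits at 0.05 each.**
- Four independent tests: 1 − 0.95⁴ = 0.1855.
- Upper bound under any dependence: 4 × 0.05 = 0.20.

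**Allowing for the actual test types.**

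The two leukocyte tests, as bivariate normal statistics, have P(at least one rejection) = 0.0975, 0.0907 and 0.0781 at ρ = 0, 0.5 and 0.8.

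The binary tests do not always use their full 0.05. Exact size with 126 and 125 patients:

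| Event rate | Fisher | Uncorrected chi-square |
|---|---|---|
| 1% | 0.003 | 0.022 |
| 2% | 0.016 | 0.045 |
| 3% | 0.025 | 0.044 |
| 5% | 0.030 | 0.048 |
| 10% | 0.037 | 0.050 |
| 15% | 0.040 | 0.051 |

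The family-wise rate is 1 − (1 − P_leuk)(1 − s_fever)(1 − s_endo), where s is the size of the binary test. Example: ρ = 0 with Fisher at 15% gives 1 − 0.9025 × 0.960² = 0.168. Over event rates from 1% to 15%:

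| ρ | Fisher | Chi-square |
|---|---|---|
| 0 | 10.3–16.8% | 13.6–18.7% |
| 0.5 | 9.6–16.2% | not tabulated; lies between the other rows |
| 0.8 | 8.4–15.0% | 11.8–16.9% |

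**Check on independence.** Simulation with 20,000 trials per scenario, t-tests for leukocytes, and a latent correlation of 0 or 0.3 of fever and endometritis with each other and with the leukocyte measures, gave 8.3–17.4% with Fisher and 11.7–19.2% with chi-square. The independence assumption matters little.

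**If 0.01 governed all four.** 1 − 0.99⁴ = 0.039, bound 0.04.

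**If a fifth primary outcome was intended.** 1 − 0.95⁵ = 0.226 for independent tests.

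**With Holm across the four at 0.05.** In the same simulation, with Fisher for the binary outcomes, the family-wise rate was 2.1–4.5%.

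**The case against.** The title and aim are about leukocytosis, and the first listed outcome is the only one defined as a change in leukocyte count, so a sympathetic reader would take it as the true primary. That is the most natural reading, but the documents never designate it, and they do not demote fever or endometritis. If only the two leukocyte outcomes were treated as primary, the rate would still be 7.8–9.7% at the correlations above.

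The error rate also depends on a rule that the plan does not state. If all four outcomes had to be significant, there would be no inflation. This is correct, and the percentages should be read as the consequence of the any-one reading, which the plan leaves open.

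The lower end is a product of the assumptions. A leukocyte correlation of 0.9 with very rare events gives about 7.0%, and the theoretical floor is 5%. Rare fever is plausible, since the protocol requires a temperature above 38.5°C on two consecutive days, excluding the first 24 hours. So 8% is not a firm minimum, though the 18.5% and 20% figures need neither a correlation nor an event rate.

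The two thresholds may be no more than two reporting levels, and the 95% interval points to 0.05 as the operative one. That is fair: it is a wording defect. The gap in the numbering may come from text extraction and carries no weight here.

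**Conclusion.** The concern holds. The plan has four primary outcomes and no rule that turns four results into one conclusion. If each is tested at 0.05 and any one counts, the chance of a false positive primary result is 18.5% for independent tests, at most 20%, and roughly 8–19% over the scenarios examined. These figures assume no true difference on any outcome, two-sided tests and a near-equal split; the range also rests on the assumed correlations and event rates. The any-one condition is essential to them. The trial can proceed, but the plan should be corrected, because as written it does not protect the interpretation of the primary result.

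**What to change.** Before any outcome is analysed by group, adopt one of two options.

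- **(a) One primary outcome.** Name a leukocyte measure that matches the aim, tested two-sided at 0.05. The change from before delivery to day 1 fits the stated aim most directly; the day-2 measure is also possible. Make the other three secondary and report them with 95% confidence intervals.
- **(b) Four primary outcomes with Holm adjustment.** Control the family-wise error at 0.05 and state that any Holm-significant outcome counts as a primary result. The ordered p-values are compared with 0.05/4 = 0.0125, 0.05/3 = 0.0167, 0.05/2 = 0.025 and 0.05.

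Under either option, state 0.05 as the single significance threshold, delete the 0.01, and correct the outcome numbering or restore the missing item.

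**Cost.** Protocol and SAP wording only. Under (a), fever and endometritis lose primary status. Under (b), each test loses some power. In the worst case, the first Holm step at 0.0125 (critical value 2.498), a test with 80% power at 0.05 falls to Φ(1.960 + 0.842 − 2.498) = 62%, and one with 90% falls to Φ(1.960 + 1.282 − 2.498) = 77%.

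### The pre-delivery leukocyte count is collected but not adjusted for, day 1 and day 2 use different outcome forms, and the effect measure is left to a normality test; the cost is precision and prespecification, not bias

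*Combined protocol and SAP*

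**What the plan says.** The Objectives section states the aim as an association between removal method and "increase in postpartum white blood cell counts". The Design section says patients are randomized between the two methods. The Methods section lists the blood counts recorded: "Complete blood count before delivery, on postpartum day 1 and 2".

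Under Primary Outcome Measure, item 1 is "Change from baseline leukocyte level at postpartum day 1". Item 2 is "Detection of leukocyte count", with the explanation "Complete blood count is measured on postpartum day 2" and no reference to baseline. The secondary outcome, blood loss, is "calculated by change from baseline hematocrit level at postpartum day 1".

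For continuous data the Statistical Analysis Plan says two things: "Kolmogorov-Smirnov test will be used for the assessment of the normality of data", and "Mann-Whitney U test will be used for the data not normally distributed". It names no regression or ANCOVA and no between-group test for normally distributed data. It mentions a 95% confidence interval without saying for which effect measure.

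**The concern.** The same biomarker, measured one day apart, is handled in two ways. A change score fixes the coefficient on the baseline count at 1, and a raw count fixes it at 0. Neither lets the data estimate it, although the baseline is available for that purpose.

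The normality check also decides what is compared. One branch leads to a rank test. The other leads to a test that is not named, presumably of means. The effect measure is therefore not settled until the data are seen, and it could differ between day 1 and day 2.

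At stake are the width of the interval for the leukocyte outcomes, mainly on day 2, and whether the two days can be read on one scale.

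**Working it through.** **The plan's own figure.** The sample size formula gives 720 × 1.96² × 0.25 / (0.05² × 719 + 1.96² × 0.25) = 691.488 / 2.7579 = 250.73, so 251 reproduces. It is a survey-precision figure and does not depend on how leukocytes are analysed. It serves below only as the total number of patients.

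**Assumptions.** The documents give no pre/post correlation (ρ), SDs or skewness. I take ρ = 0.3, 0.5 and 0.7. I set the pre-delivery SD to 1 and the post-delivery SD to k = 1, 1.25 or 1.5. For power, 251 is split 126/125 (equal allocation is assumed), with two-sided alpha 0.05.

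**Variance of the arm comparison, up to a common factor**
- Raw count: k²
- Change score: k² + 1 − 2ρk
- Linear baseline adjustment (ANCOVA): k²(1 − ρ²)

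**Day 2, adjustment against the raw count.** The reduction is ρ², whatever k is: 9%, 25%, 49%. At ρ = 0.5, a raw-count analysis would need about 251 / 0.75 = 335 patients to match ANCOVA with 251.

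**Day 1, adjustment against the change score**

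| k | ρ = 0.3 | ρ = 0.5 | ρ = 0.7 |
|---|---|---|---|
| 1 | 35% | 25% | 15% |
| 1.25 | 22% | 11% | 2% |
| 1.5 | 13% | 4% | 0.2% |

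For example, at k = 1.5 and ρ = 0.7 the change score has 2.25 + 1 − 2.1 = 1.15 and ANCOVA has 2.25 × 0.51 = 1.1475, a reduction of 0.2%.

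**As power, for normal counts where an unadjusted t-test would have 80%** (the t-test is an assumption, since the plan names none). Untransformed ANCOVA has about 84/90/97% on day 2 at ρ = 0.3/0.5/0.7. On day 1 it has 94/90/86% (k = 1), 89/84/81% (k = 1.25) and 85/81/80% (k = 1.5).

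**Choice of scale.** These day-2 counts are simulated as lognormal with log-SD 0.3/0.5/0.7 (skewness about 0.95/1.75/2.9), in a setting where Mann-Whitney has 80% power.
- Log-scale ANCOVA has about 86/91/98% at ρ = 0.3/0.5/0.7 for a multiplicative effect. For an additive shift it has at least 86/92/98%.
- Untransformed ANCOVA at ρ = 0.3 has 84/80/75% across the three skewness levels for a multiplicative effect, but 78/65/47% for an additive shift.

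**Price of the log scale if counts are normal and the effect is additive.** Day 1 was simulated with post-delivery mean and SD both scaled by the same ratio, and compared with a t-test on change at 80%. At coefficient of variation (CV) 0.30, the log model has about 72 to 74% at ρ = 0.7 with ratio 1.3. It has about 75 to 77% at ρ = 0.5 with ratio 1.5. Losses elsewhere were usually 0 to 4 points.

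**The normality switch.** A Lilliefors-corrected Kolmogorov-Smirnov test was applied in each arm, followed by Mann-Whitney or a t-test, in 2,000 runs per setting. Normality was rejected in at least one arm in 7% of runs with normal data, and in 53%, 87% and 98% with lognormal data at log-SD 0.2, 0.3 and 0.4. Overall type I error stayed between 4.7% and 5.7%.

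**The case against.** The strongest reply is that nothing here is invalid. In a randomized trial, a change score and a raw count are both legitimate outcomes, and unadjusted comparisons of either are unbiased. That stands.

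A reader might infer that the day-2 outcome cannot address the stated aim because it ignores baseline. The documents do not support this. Randomization makes the expected pre-delivery count equal in both arms, so the expected difference in day-2 count equals the expected difference in increase. The raw count answers the question less precisely. It does not describe the rise within each arm, but the recorded baseline allows that to be shown.

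A reader might also infer that choosing the test by Kolmogorov-Smirnov inflates false positives. The simulation shows no material inflation. The objection to the switch is that it leaves the effect measure open.

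Two further objections stand in part. First, the gain rests on assumed correlations and SD ratios, and on day 1 it may be almost nil. Second, the day-1 variance reductions above compare adjustment and change on one and the same scale. They do not guarantee that a log model beats an absolute change in cells, and with normal counts and an additive effect it can do worse. The log scale is a judgement made without distributional information in the documents, so the untransformed model should be reported beside it.

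**Conclusion.** The point holds as one of efficiency and prespecification, and it should be addressed. The facts are plain in the text: baseline is collected, day 1 is a change, day 2 is a raw count, no adjusted analysis is planned, and the only between-group test for continuous data is conditional on a normality result.

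The likely gain is on day 2, at ρ² of the variance. On day 1 it ranges from substantial to negligible, depending on ρ and k. Neither bias nor type I error inflation is claimed. All sizes are illustrative because they rest on an assumed ρ, SD ratio and distribution. The direction for linear adjustment on a given scale does not depend on those values: apart from the one degree of freedom spent on the covariate, its variance is never above that of either unadjusted form.

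**What to change.** For day 1 and day 2 separately, prespecify a linear model of log leukocyte count on arm, with log pre-delivery count as covariate. Report the adjusted ratio of geometric means with its 95% CI, and show mean change in cells per arm descriptively. Drop the Kolmogorov-Smirnov switch for these outcomes. Keep two sensitivity analyses: Mann-Whitney, and an untransformed ANCOVA giving the adjusted mean difference. As an optional extension, day-1 hematocrit can be adjusted for its own baseline, untransformed. The fever and endometritis analyses are not affected.

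The cost is a few lines of plan wording. No new data are needed, and the named software can fit the model. There are two downsides to accept knowingly. The tested effect becomes a ratio, where outcome 1 is now an absolute change. And if counts are normal with an additive effect, day-1 power can fall below that of a t-test on change, at worst in the simulations by about 8 points (about 72% against 80%, at CV 0.30, ρ = 0.7, and post-delivery mean and SD 1.3 times pre-delivery).
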